### **Other efficacy objectives**

- To evaluate the effect of serelaxin as compared to placebo on reducing time to moderate or marked improvements in dyspnea assessed by Likert scale through Day 5
- To evaluate the effect of serelaxin as compared to placebo on changes of dyspnea by VAS-AUC through Day 5
- To evaluate the effect of serelaxin as compared to placebo on reducing the time in index ICU/CCU through Day 5
- To evaluate the effect of serelaxin as compared to placebo on prevention of renal dysfunction or worsening of renal function through Day 5
- To evaluate the effect of serelaxin as compared to placebo on reducing the time to re-hospitalization due to HF and renal failure through Day 180
- To evaluate the effect of serelaxin as compared to placebo on reducing the composite endpoint of CV death or re-hospitalization due to HF/renal failure through Day 180
- To evaluate the effect of serelaxin as compared to placebo on time to in-hospital worsening heart failure through Day 5 where the in-hospital worsening heart failure is defined by symptoms only, signs only, and both symptoms and signs
- To evaluate the effect of serelaxin as compared to placebo on reducing the total intravenous loop diuretic dose, vasoactive and inotropes drug usage through Day 5
- To evaluate the effect of serelaxin as compared to placebo on the changes from baseline in cardio-renal biomarkers on Days 2 and 5

[figure not shown]

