### 4.1 Inclusion criteria

Subjects must fulfill all of the following criteria at screening to be eligible for the study. The screening period is defined as that interval that begins at the time the informed consent is signed and ends with the qualification of the subject for entry into the study (i.e. when subject is determined to meet all eligibility criteria):

1. Written informed consent must be obtained before any study-specific assessment is performed\*
2. Male or female  $\geq 18$  years of age, with body weight  $\geq 30$ kg and  $\leq 160$  kg
3. Hospitalized for AHF; AHF is defined as including all of the following measured at any time between presentation (including the emergency department and outpatient clinic) and the end of screening:
  - Persistent dyspnea at rest or with minimal exertion at screening and at the time of randomization
  - Pulmonary congestion on chest radiograph
  - BNP  $\geq 500$  pg/mL or NT-proBNP  $\geq 2,000$  pg/mL
4. Systolic BP  $\geq 125$  mmHg at the start and at the end of screening

5. Able to be randomized within 16 hours from presentation to the hospital, including the emergency department and outpatient clinic.
6. Received intravenous furosemide of at least 40 mg total (or equivalent) at any time between presentation (this includes outpatient clinic, ambulance, or hospital including emergency department) and the start of screening for the study for the treatment of the current acute HF episode
7. Impaired renal function defined as an eGFR between presentation and randomization of  $\geq 25$  and  $\leq 75\text{mL/min}/1.73\text{m}^2$ , calculated using the sMDRD formula (or modified sMDRD formula according to specific ethnic groups and local practice guidelines). ([Levey et al 2006](#); [Ma et al 2006](#); [Matsuo et al 2009](#); [Townamchai et al 2013](#)).

\* *Patient assessments of AHF that are per current local institutional/hospital standard protocol or part of routine clinical care that are performed within 16 hours from presentation are allowed before signing informed consent, and can be used to support patient screening.*

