### **Other efficacy variables**

Other efficacy variables will comprise:

1. Time to moderate or marked improvements in dyspnea by Likert scale through Day 5
2. Dyspnea by VAS-AUC changes through Day 5
3. Length of stay in index ICU/CCU
4. Renal dysfunction & prevention of in-hospital worsening of renal function through Day 5
5. Time to re-hospitalization due to HF and renal failure through Day 180
6. Time to CV death or re-hospitalization due to HF/RF through Day 180
7. Time to in-hospital worsening heart failure through Day 5 where the in-hospital worsening heart failure is defined by symptoms only, signs only, and by both symptoms and signs
8. Use of loop diuretics and vasoactive agents through Day 5
9. Changes in cardio-renal biomarkers (Days 2 and 5)

Time to moderate or marked improvements in dyspnea by Likert scale through Day 5 (variable number 1) will be analyzed by Wilcoxon rank-sum test. Other time to event variables (5, 6 and 7) will be analyzed by presenting Kaplan-Meier estimates and testing with the log rank test. Change from baseline variables (2) will be analyzed using ANCOVA model with baseline VAS as a covariate. Variables representing the number of days or multi-categorical variables (3) will be analyzed using the Wilcoxon rank-sum test. The categorical variables (4 and 8) will be analyzed using chi-squared tests.

Detailed biomarker analyses (9) (changes in cardio-renal biomarkers at Days 2 and 5) will be included in the Statistical Analysis Plan.

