2.1.10 Concomitant medications, surgical and medical procedures

Unless specified, the use of all concomitant medications will be summarized using the SAF population.

Major cardiovascular and non-cardiovascular classes of medication taken by a subject approximately 30 days prior to study drug initiation and on a daily basis while hospitalized through Day 5, at Discharge, and at Day 14 and other follow-up visits will be recorded. At each visit, only those medications currently being taken or those were taken within 24 hours prior to the given visit will be collected. These medications are predefined by the code lists and will be collected in each of following eCRFs:

- IV loop diuretic medications for heart failure (collected since initial presentation of HF)
- IV medications other than loop diuretics (collected since initial presentation of HF)
- Other non-IV prior medications (30 day prior to screening, within 24 hours at each visit)
- Other prior and concomitant medications

IV loop diuretic medications

IV loop diuretic medications for heart failure include Bumetanide, Etacrynic acid, Ethacrynic acid, Furosemide, Torasemide, Torsemide and Piretanide.

The number and percentage of subjects using each medication will be summarized by protocol scheduled time point. Each time point reflects medication use within the preceding 24 hours.

The total daily dose for each medication will also be presented at each time point. In addition, cumulative use (total dose as the sum from Day 1) at 48 hours (24 hours/Day 1 and 48 hours/Day 2), and at Day 5 (from 24 hours/Day 1 to Day 5) in furosemide equivalent (mg) will be summarized. The calculation of furosemide equivalents (mg) for Bumetanide, Etacrynic acid/Ethacrynic acid, Torsemide/Torsemide acid and Piretanide are actual dose (mg) multiplied by constant 40, 0.8, 2, or 6.67, respectively.

Doses will be imputed as zero for study days where no use was reported.

IV medications other than loop diuretics

Other IV medications include not limited to Dopamine, Dobutamine, Milrinone, Enoximone, Norepinephrine, Epinephrine, Nesiritide, Levosimendan, Isosorbide Dinitrate, Nitroglycerin, Nitroprusside, Phenylephrine, Caperitide and Other (including but not limited to Danshen).

The number of subjects using each medication will be presented in the same way as IV loop diuretic medications.

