The average dose over the time administered of the medication will be presented separately for each medication at each reported time point. No equivalent dose unit among other IV medications will be converted.

Note that the frequency (number and percentage) of subjects using IV loop diuretic and vasoactive agents through Day 5 is an efficacy endpoint and it's discussed in [Section 2.2.3](#).

Other non-IV prior medications & other non-IV medications

The number and percentage of subjects using other non-IV medications will be summarized for each of the time periods for general, ACE inhibitor (ACEi), angiotensin inhibitor (ARB), ACEi or ARB, beta blocker, PO loop diuretics, other PO diuretics, calcium channel blockers, aldosterone antagonist and cardiac glycosides.

The number (%) of subjects who have these medications initiated during their index hospitalization and subjects who have these medications increased during the period following discharge from the index hospitalization will also be presented.

The average daily dose administered will be summarized at each time point for each medication within the loop diuretics, ACEi, ARB, beta blocker, aldosterone antagonist, ARNi and direct renin inhibitor.

Other non-IV medications taken prior to and after the start of study drug will be presented by the ATC and preferred terms.

Other prior and concomitant medications

All other concomitant medications (not included in above classes) and significant non-drug therapies, 30 days prior to screening and ongoing basis until subjects completed or discontinued from the study, will be summarized respectively by ATC therapeutic class, preferred term, and treatment group for the SAF population.

Alternative medicine or herbal medicine will also be presented for the SAF population.

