Time to rehospitalization due to heart failure (HF) or renal failure (RF) through Day 180

Time-to-event (in days) will be calculated using time of first event of adjudicated rehospitalization due to HF or RF minus time of randomization. If the reason for adjudicated rehospitalization is unknown, it will be considered as the event.

The analysis and censoring method will be performed similarly to time-to-all-cause-death.

Due to competing risk between death and rehospitalization, the difference in mortality between the treatment groups may mislead the results. In this case, the composite endpoint of Time to CV death or rehospitalization due to heart failure (HF)/renal failure (RF) through Day 180 provides more reliable results.

Time to in-hospital worsening heart failure through Day 5 by symptoms and signs

Time-to-event (in days) will be calculated using time of first event of in-hospital worsening heart failure through Day 5. The worsening heart failure is defined by symptoms only, signs only, and by both symptoms and signs. The analysis and censoring method will be performed similarly to time-to-WHF.

Use of IV loop diuretic and vasoactive agents through Day 5

The subjects with intravenous diuretic and vasoactive therapy (yes/no) during 5 days after study medication infusion will be analyzed using chi-squared test.

The medications of interest are collected in two eCRF pages: “IV loop diuretic medications for heart failure” and “IV medications other than loop diuretics” ([Section 2.1.10](#)). The summaries of doses for those medications are also addressed in [Section 2.1.10](#).

Change from baseline in cardio-renal biomarkers through Day 2 and Day 5

Biomarkers related to cardiac and renal function/injury including but not limited to high sensitivity troponin T, NT-proBNP, and Cystatin C will be collected at baseline, at 48 hours (Day 2) and 120 hours (Day 5) post infusion. This list of potential biomarkers may be changed or expanded further as it is recognized that more relevant or novel biomarkers may be discovered.

Details are described in the separate biomarker statistical analysis plan.

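### The objective is a lower total IV loop diuretic dose, but the only planned between-arm test is on any use (yes/no), which cannot detect a lower dose among users

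*SAP*

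**What the plan says.** Protocol 2.2 (Other efficacy objectives) and the synopsis state the objective as "reducing the total intravenous loop diuretic dose, vasoactive and inotropes drug usage through Day 5". It speaks of dose for loop diuretics and of usage for vasoactive and inotropic drugs.

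The endpoint lists (Protocol 6.4.2 and 9.5.1, SAP Table 2-5 row 8) shorten this to use of loop diuretics and vasoactive agents, and dose drops out. Protocol 9.5.1 then says "The categorical variables (4 and 8) will be analyzed using chi-squared tests", where variable 8 is this endpoint. SAP 2.2.3 specifies the yes/no form: "The subjects with intravenous diuretic and vasoactive therapy (yes/no) during 5 days after study medication infusion will be analyzed using chi-squared test". SAP 2.1.10 confirms that "the frequency (number and percentage) of subjects using IV loop diuretic and vasoactive agents through Day 5 is an efficacy endpoint".

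Dose is handled in SAP 2.1.10, among the concomitant medications. Doses are converted to furosemide equivalents, and the plan summarises "cumulative use (total dose as the sum from Day 1) at 48 hours (24 hours/Day 1 and 48 hours/Day 2), and at Day 5". SAP 2.2.3 points the reader there. The default population in that section is the SAF, whereas SAP 2.2 makes the FAS primary for efficacy. On missing days it says: "Doses will be imputed as zero for study days where no use was reported".

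**The concern.** The test and the objective concern different quantities. An any-use indicator changes only when a patient goes from some IV loop diuretic to none. An effect that lets patients manage on less, which is what the objective describes, leaves it unchanged. Followed as written, the plan could report a null result for this objective when dose had fallen materially.

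The dose itself gets no between-arm estimate, confidence interval or test. Anyone wanting to address the objective would have to choose a dose analysis after unblinding, or read the descriptive summary as evidence. That summary is on a different population from the other efficacy analyses. It also sets dose to zero on days with no reported use and makes no exception for death, so as written a patient who dies early can appear to have needed little diuretic.

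**Working it through.** **1. The plan's own figure.** The documents give no power, expected rate or dose spread for this endpoint. The only stated figure is the total of 1,520 (Protocol 9.7, SAP 2.7), which supplies the 760 per arm used below. Inputs: placebo failure 11.9% and success 26.0% (Protocol 6.4.3), so unchanged is 100 − 11.9 − 26.0 = 62.1%; odds ratio 0.75; two-sided 5%; 80% power. The Whitehead formula is

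N = 12(z₀.₉₇₅ + z₀.₈)² / {(ln OR)² (1 − Σp̄³)}.

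Applying the odds ratio gives serelaxin proportions of 9.2 / 58.9 / 31.9%. The averages are 0.1055, 0.6050 and 0.2895, with Σp̄³ = 0.2469. Then N = 12 × 7.849 / (0.08276 × 0.7531) = 1,511, within 0.6% of 1,520. The trial's sample size reproduces and this point does not affect it.

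**2. Why the yes/no test cannot see a dose effect.** Let D be a patient's total dose and U = 1 if D > 0. If treatment multiplies dose by r > 0, then U is the same for rD as for D. The chi-squared statistic depends only on the two use rates. With equal use it rejects at its alpha level, whatever r is and whatever the common use rate is. No assumption about use is needed.

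**3. Illustration.** Assumptions, none from the documents: 760 per arm, equal use in both arms, dose among users lognormal with coefficient of variation (CV) 0.8 or 1.2, dose ratio 0.80, zero for non-users, no deaths, two-sided 5%, 1,000 runs per cell.

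| Use rate | CV | Chi-squared, any use | Rank-sum, dose | t-test, dose |
|---|---|---|---|---|
| 80% | 0.8 | 0.035 | 0.967 | 0.988 |
| 80% | 1.2 | 0.054 | 0.846 | 0.871 |
| 90% | 0.8 | 0.048 | 1.000 | 0.997 |
| 90% | 1.2 | 0.058 | 0.944 | 0.917 |
| 95% | 0.8 | 0.042 | 1.000 | 0.998 |
| 95% | 1.2 | 0.056 | 0.981 | 0.927 |
| 99% | 0.8 | 0.040 | 1.000 | 0.999 |
| 99% | 1.2 | 0.042 | 0.992 | 0.943 |

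The Monte Carlo error of a 5% rate is √(0.05 × 0.95 / 1000) = 0.7 points, so the chi-squared column is its alpha level. More generally, a comparison of mean dose with 760 per arm has 80% power for a standardised difference of 2.802 × √(2/760) = 0.144.

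**4. What the yes/no test can detect.** It detects a change in the proportion of users. Power = Φ[(d − 1.96·SE₀)/SE₁], where d is the difference in use, SE₀ = √{2p̄(1 − p̄)/760} and SE₁ = √{[p₁(1 − p₁) + p₂(1 − p₂)]/760}. Solving for 80% power:

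| Assumed placebo use | Smallest detectable absolute reduction |
|---|---|
| 70% | 6.8 points |
| 80% | 6.1 points |
| 90% | 4.7 points |
| 95% | 3.6 points |
| 98% | 2.6 points |
| 99% | 2.0 points |

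**5. Deaths under the zero rule.** Dose given before death still counts, and later days have no reported use, so the rule read literally scores them zero. Neighbouring endpoints in SAP 2.2.3 treat death as a bad outcome: VAS-AUC carries forward the worst observed score from the day of death, and ICU/CCU stay assigns the maximum number of days. The documents give no Day 5 death rate. The whole failure composite in RELAX-AHF was 11.9% and 6.4%, so deaths there were at most 0.119 × 760 ≈ 90 and 0.064 × 760 ≈ 49 when scaled to this trial's arms. Worsening heart failure and re-hospitalisation are included in those ceilings.

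**The case against.** A reader might infer a stronger point: that nearly every patient in both arms will be a yes, because entry requires IV furosemide ("Received intravenous furosemide of at least 40 mg total (or equivalent"). The documents do not support this. The entry dose is given before the start of screening and lies outside the yes/no window. Later IV furosemide is allowed but not required (Protocol 5.5.7), background care may be intravenous or oral (Protocol 5.1.2), and no post-baseline use rate is given. High use is plausible in patients admitted with congestion, but it is an assumption. Nor does high use in itself remove power: the detectable difference in step 4 shrinks as use rises. Setting low power for a 1- or 2-point fall in use against high power for some fall in dose would also prove little, since nothing in the documents links the two effects. The point does not need any of this, because the mismatch holds at any use rate.

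More can fairly be said for the plan:

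- The dose is not ignored. SAP 2.2.3 refers to the dose summaries, so the gap is a missing between-arm analysis of a derived variable.
- The SAP follows the protocol, which itself prescribes chi-squared.
- Yes/no suits the vasoactive and inotrope part of the objective.
- Zero is a sensible value for a living patient with no IV diuretic reported. The SAP does not expressly apply it to days after death, and such deaths are probably few.
- This is item 8 of nine other efficacy endpoints, with no multiplicity adjustment.

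All of these stand. They limit the scope and the severity. None supplies a comparison of dose.

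**Conclusion.** The point holds for the loop-diuretic part of the objective. That the yes/no test cannot detect a lower dose among users follows from the endpoint's definition and needs no assumption. The rank-sum power of 0.85 to 1.00 is illustrative and rests on the assumed 20% reduction, use rates and CVs. The treatment of early deaths is a real gap in the wording, but its effect cannot be sized from the documents.

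Severity is low to moderate. The sample size, the primary result, the testing hierarchy and the safety conclusions are unaffected. What is at risk is one named protocol objective, which would otherwise be answered by a test of something else or by an analysis chosen after unblinding.

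**What to change.** Amend SAP 2.2.3 and Table 2-5 row 8, and Protocol 9.5.1 (variable 8) so that the two documents agree:

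- **Loop diuretics:** analyse cumulative IV furosemide-equivalent dose through Day 5 in the FAS by Wilcoxon rank-sum test, with an estimated difference (for example Hodges–Lehmann) and 95% confidence interval.
- **Deaths by Day 5:** assign the worst rank, in line with the SAP's handling of deaths for VAS-AUC and ICU/CCU stay. Keep zero for living patients on days with no reported use, and say in SAP 2.1.10 that the zero rule does not extend past death for this analysis.
- **Vasoactive and inotropic agents:** keep chi-squared on yes/no, reported separately from diuretics. This also settles whether the present yes/no variable combines the two classes.
- **Window:** use one definition. SAP 2.2.3 counts five days after infusion, while the objective runs through Day 5.

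The cost is wording in both documents and one analysis of a variable already derived. No new data are needed. The change should be made before unblinding.

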2.3 Pharmacokinetic evaluations

All subjects with at least one available valid (i.e. not flagged for exclusion) PK concentration measurement, who received serelaxin infusion and experienced no protocol deviations with relevant impact on PK data will be included in the pharmacokinetic (PK) data analysis. Steady state concentration (Css) will be estimated based on the serum concentration determined at the 48 hour time point prior to the end of infusion. Systemic clearance will be calculated using the rate of infusion and Css for each subject as indicated below:

$$\text{Clearance (mL/hr/kg)} = \text{Rate of infusion (\mu g/kg/hr)} / \text{Css (\mu g/mL)}$$

Where the rate of infusion is the actual dosing rate calculated as below for each individual subject:

$$\text{Rate} = \frac{\text{VolRLX}}{\text{VolRLX} + \text{VolSol}} \times \frac{\text{ConcRLX}}{\mu\text{g/mL}} \times \frac{\text{Flow}}{\text{mL/hr}} \times \frac{24}{\text{hrs/day}} / \frac{\text{Weight}}{\text{kg}}$$

where VolRLX is the volume of serelaxin drawn from the vials and added to a volume VolSol of the solution contained in the infusion bag, ConRLX is the concentration of the serelaxin stock solution in the vial (1000 $\mu\text{g/mL}$), Flow is the flow rate of the solution from the infusion bag, and Weight is the body weight measured at Day 1 pre-dose baseline. Since only sparse PK time points for serelaxin serum concentration will be collected, no other PK parameters will be determined in this study.

Missing values or those below the assay LLOQ (BLQ) will be indicated in the data listings and treated as zero for PK parameter calculations and presentation.

Descriptive statistics for serelaxin concentrations will be listed by time points (for baseline and 48hr samples only) to include arithmetic mean, geometric mean with its corresponding 90% confidence interval, median, SD, CV, min and max. A value of "0" will be used for samples that are BLQ in these calculations and therefore be excluded from geometric mean calculations. Descriptive statistics include arithmetic mean, geometric mean with its corresponding 90% confidence interval, median, SD, CV, min and max will also be provided for the two PK parameters, Css and clearance (CL).

Subgroup analysis on Css and CL to assess the potential effects of various extrinsic and intrinsic factors on the PK of serelaxin may be performed as appropriate. These factors may include but not limited to renal function (e.g. eGFR), age, gender, race or ethnicity, country, concomitant medications, etc.

Serelaxin serum concentration will be assayed in Day 60 samples as well, in order to demonstrate the lack of drug interference with the immunogenicity assay. This data will be included only as part of the immunogenicity results but not in the PK results (see [Section 2.6.3](#)).

